It is known from many research studies that human performance declines with insufficient or disrupted sleep causing loss of cognitive and behavioral flexibility together with reduction in attention that produces errors on the work environment with consequences sometimes severe (1). Moreover it has been shown in the past years that sleep disruption may have wide-ranging effects on the cardiovascular, endocrine, immune, and nervous systems such as obesity, diabetes and impaired glucose tolerance, hypertension and other cardiovascular diseases, anxiety symptoms, depressed mood and alcohol use (2).

According to the *Sleep in America* survey from the National Sleep Foundation, two of the top five issues associated with disrupted sleep in adults are *inside* and *outside noise* (3). Indoor and outdoor noises can prevent sleep consolidation by increasing the wake-after-sleep-onset (WASO) time or increasing the number of brief *arousals* (3 to 15 seconds) from sleep.

One possible approach to improve sleep quality in the general population is to reduce the impact of indoor and outdoor noise. Stanchina and coworkers (4) recently proved in an Intensive Care Unit setting that application of mixed frequency sound noise (62 DB) in patients' room reduced the numbers of arousals from sleep by increasing the acoustic arousal threshold. These authors also showed that the change in noise level from baseline is more important than the peak noise level in determining the arousal from sleep.

Another study showed that application of constant noise (40 to 60 DB) during the night could increase stable sleep when measured with a technique called cardiopulmonary coupling. This method is designed to assess sleep stability using a measure derived from the ECG recording (5).

Although these and others studies showed a possible relationship between exposure to overnight constant noise of mixed frequency sounds and sleep quality, no study performed a complete assessment of all the sleep variables that determine sleep quality in the clinical setting.

II. SPECIFIC AIMS

To determine the effect of mixed frequency sound on subjective and objective sleep quality.

We hypothesize that the exposure to sound during sleep will improve sleep quality and will reduce sleep onset latency.

Specifically, we will test this hypothesis by assessing;

The effect of exposure to a range of frequencies from 350 to 4000Hz at a pressure level of 40dB on subjective sleep quality scores, sleep onset latency, sleep architecture (time spent in rapid eye movement (REM) and non-REM (NREM) sleep stage 1, 2, 3), number of arousals from sleep and time of wakefulness after sleep onset in a group of healthy subjects.

III. SUBJECT SELECTION

We will recruit a group of 20 healthy controls aged 21 to 65 years old. Normal controls will be recruited from the community, as well as from our existing database of control subjects, and will be completely healthy and thus without medical or sleep problems.

PARTNERS HUMAN RESEARCH COMMITTEE DETAILED PROTOCOL

Version: March 15, 2016

Exclusion criteria:

- Individual affected by insomnia or other sleep-related diseases.
- Individual taking any medication known to influence sleep/arousal state

Equal number of males and females will be recruited. We will consider all applicants regardless of sex, race, color, creed, or national origin.

IV. SUBJECT ENROLLMENT

Subjects will be recruited through email, telephone, newspaper, and or bulletin advertisements. Only subjects who have stated in the initial clinical questionnaire that they are interested in hearing about research studies will be contacted by phone. Should the subject be interested in the study, they can call the study physician or coordinator to inquire about study participation. We will also recruit from our existing database of research participants.

Subjects who respond will be given a thorough review of the risks, discomforts, potential benefits to the study and their expected involvement using a prepared script approved by our Institutional Review Board. Subjects will be given a copy of the informed consent and allowed a minimum of 24 hours to review the information and make a decision on study participation. During this time, the subject will have the opportunity to discuss the research with his/her primary care physician or clinician. The study investigators will be available to answer any questions should any arise. Informed consent will be obtained from all subjects by the principal investigator or a co-investigator prior to commencement of any study procedures. Subjects will be informed that they may withdraw from the study at any point, with no impact on their ongoing care.

Inclusion and exclusion criteria will be carefully assessed prior to enrollment. Assuming subjects meet the inclusion criteria, they will begin the protocol by scheduling their overnight studies in the clinical/physiology laboratories. Subjects will be informed that they may withdraw from the study at any point, with no impact on their ongoing care. We have not previously had difficulty enrolling participants into similar studies performed in our laboratory.

V. STUDY PROCEDURES

Protocol:

The protocol will be composed by 2 overnight sleep studies (a night with no noise and a night with background noise) to be conducted at Brigham and Women's Hospital. The 2 nights will be performed approximately one week apart in random order. Sleep will be scored by an expert sleep technologist blinded to the randomization order. Pittsburgh Sleep Quality Index questionnaire will be administered to all study participants before sleep on the first study night. Stanford Sleepiness Scale score and a subjective sleep quality score will be obtained from every subject after each study night.

Measurements and equipment:

Subjects will be instrumented with standard polysomnography (PSG) recording sensors. Sleep stage and arousals will be measured with electrodes pasted on to the scalp, face, chin and chest (EEG, EOG, EKG, chin EMG). Paste-on EMG electrodes will be placed over the anterior tibialis muscle to detect leg

PARTNERS HUMAN RESEARCH COMMITTEE DETAILED PROTOCOL

Version: March 15, 2016

movements. Respiratory effort belts will be placed around the chest and abdomen to measure breathing movements. Oxygen saturation will be measured continuously with a pulse oximetry probe placed on either the fingertip or earlobe. Snoring will be detected with a small microphone positioned over the suprasternal notch. Body position will be recorded with a sensor taped to the thoracic belt. Each of these devices is standard for diagnostic PSG and should not be uncomfortable.

The mixed frequencies noise background will be delivered by four speakers included in two wall mount modules powered by A/C and will include a range of frequencies from 350 to 4000Hz at a pressure level of 40dB (Nightingale, Cambridge Sound Management). The system will be activated at “lights off” time via computer by a co-investigator or a trained student who will monitor patients and data recordings overnight.

Data Analysis:

Sleep will be scored by an expert sleep technologist blinded to the randomization order following American Academy of Sleep Medicine rules.

If the data collected will be considered insufficient, the subject will be asked to repeat the whole study or a part of it without signing a new informed consent form.

Reimbursement

Subjects will receive \$100/night for participation in each overnight study (TOTAL = \$200).

Reimbursement for parking expenses will be provided.

If the subjects will repeat a part or the entire protocol because of insufficient data collection, they will be reimbursed \$100 for any extra night.

VI. BIOSTATISTICAL ANALYSIS

In this protocol we want to collect pilot data to measure the possible size effect of this intervention. Variables of interest will be compared using a Student T-test with $p<0.05$ considered as statistically significant.

VII. RISKS AND DISCOMFORTS

We believe that the risks associated with participation in this study are minimal. All study procedures have been conducted in our laboratory without serious incident. Anticipated risks and discomforts are listed below:

1. The equipment used for assessing sleep (paste on electrodes) is standard and poses no risk. The electrodes may be mildly uncomfortable and could cause some sleep interruption. Thus subjects may feel somewhat tired the day following this study.
2. The background noise could cause sleep disruption and mild discomfort at wake-to-sleep transition. In case the subject will not tolerate the noise we will reduce the intensity or stop the noisy signal.

PARTNERS HUMAN RESEARCH COMMITTEE DETAILED PROTOCOL

Version: March 15, 2016

VIII. POTENTIAL BENEFITS

Although it is unlikely that there will be any direct physical benefit to the subjects from participating in this study, we will make known to each subject, if requested, some of the information we have gathered from this physiologic testing. This study provides a unique opportunity to gain insight into the specific mechanisms by which continuous background noise may improve sleep quality. The results may, in the future, lead to improved strategies for the treatment of insomnia. However, if previously unknown abnormalities of sleep are encountered, this information will be passed onto the subject. Results can be forwarded to the primary care physician or clinician at the request of the subject.

IX. MONITORING AND QUALITY ASSURANCE

As this study is a physiological investigation and not clinical trial, a formal Data and Safety Monitoring Board will not be implemented. The PI will be responsible for monitoring safety and quality assurance. Additionally, the ongoing results, problems, and limitations of the study will be presented on a regular basis to the investigators in the Division of Sleep Medicine. Any adverse events will be promptly reported to the Human Research Committee for review according to HRC guidelines.

Adequacy of Protection Against Risks

All of our laboratory personnel involved in the research of human subjects have completed the required institutional program for education in the protection of human research participants and their confidentiality. The institutional educational program consists of the review of regulatory and informational documents pertaining to human-subject research, passing a test demonstrating knowledge of the ethical principles and regulations governing human-subject research and signing a statement of commitment to the protection of human subjects.

All electronic data will be stored on secure computers under password protection with no access allowed to individuals outside of our research team. All paper data will be stored under lock and key with access only given to the study staff.

Protection Against Risks

We believe that all possible safeguards are in place to minimize the risk. However, several steps will be taken to insure patient comfort and safety. We will work with our IRB to come up with a safety monitoring plan to minimize risk and discomfort. This will include:

- Reporting any complications of our studies immediately to the IRB.
- Appoint a safety officer ([name]) who will work with our physicians and technicians to maximize safety and comfort.

The study coordinator will meet with the safety officer and PI monthly (and as needed) to go over any complaints or problems. The safety officer will call the patients with problems directly to verify important issues. If problems are identified, the protocol will be adjusted as needed. Based on conversations with the NIH and the NHLBI policy (<http://www.nhlbi.nih.gov/funding/ethics.htm>), we will not require a

PARTNERS HUMAN RESEARCH COMMITTEE DETAILED PROTOCOL

Version: March 15, 2016

formal data safety monitoring board. However, we do have a thorough data safety monitoring plan whereby our safety officer will review all adverse events in order to classify them as serious adverse events, minor adverse events, and whether they are anticipated or unanticipated, and study related or unrelated as per our IRB rules and the NHLBI policy. The medical monitor will be an academic physician with considerable experience in clinical research but not involved in our research program or a co-investigator in any of our studies. The medical monitor will strictly adhere to the following definitions:

Definitions

Definitions are per January 2007 OHRP *Guidance on Reviewing and Reporting Unanticipated Problems Involving Risks to Subjects or Others and Adverse Events, OHRP Guidance*, <http://www.hhs.gov/ohrp/policy/AdvEvntGuid.htm>

Adverse Event (AE): any untoward or unfavorable medical occurrence in a human subject, including any abnormal sign (for example, abnormal physical exam or laboratory finding), symptom, or disease, temporally associated with the subject's participation in the research, whether or not considered related to the subject's participation in the research.

Serious adverse event (SAE): any adverse event that:

- Results in death
- Is life threatening, or places the subject at immediate risk of death from the event as it occurred
- Requires or prolongs hospitalization
- Causes persistent or significant disability or incapacity
- Results in congenital anomalies or birth defects
- Is another condition which investigators judge to represent significant hazards

Unanticipated Problem (UP): any incident, experience, or outcome that meets all of the following criteria:

- unexpected, in terms of nature, severity, or frequency, given the research procedures that are described in the protocol-related documents, such as the IRB-approved research protocol and informed consent document; and the characteristics of the subject population being studied;
- related or possibly related to participation in the research, in this guidance document, possibly related means there is a reasonable possibility that the incident, experience, or outcome may have been caused by the procedures involved in the research;
- suggests that the research places subjects or others at a greater risk of harm (including physical, psychological, economic, or social harm) than was previously known or recognized.

Adverse Events (FDA) versus Unanticipated Problems (OHRP)

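### Does the plan need a written procedure to keep the sleep scorer from learning which night had the sound?

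*Combined protocol and SAP*

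**What the plan says.** Section V (Study Procedures, Protocol) describes two laboratory nights about a week apart in random order, one with the sound and one without. It states: "Sleep will be scored by an expert sleep technologist blinded to the randomization order". The Data Analysis paragraph of the same section repeats the commitment and adds the scoring standard: "blinded to the randomization order following American Academy of Sleep Medicine rules".

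Three other places bear on whether the masking could fail:

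- Section V, Measurements and equipment, on the montage: "Snoring will be detected with a small microphone positioned over the suprasternal notch".
- The same paragraphs, on the operator, who starts the sound at lights off "via computer by a co-investigator or a trained student who will monitor patients and data recordings overnight".
- Section VII (Risks and Discomforts): "In case the subject will not tolerate the noise we will reduce the intensity or stop the noisy signal".

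The signals named for staging and arousals are listed separately: "Sleep stage and arousals will be measured with electrodes pasted on to the scalp, face, chin and chest (EEG, EOG, EKG, chin EMG". The microphone is not among them.

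**The concern.** Subjects hear the sound and the operator knows the condition, so masked scoring is the only stated protection against knowledge of condition for sleep onset latency, time in each stage, arousals and wake after sleep onset. The hypothesis has a direction: "We hypothesize that the exposure to sound during sleep will improve sleep quality and will reduce sleep onset latency". The stated product is an effect size: "In this protocol we want to collect pilot data to measure the possible size effect of this intervention". A scorer who knew the condition and leaned towards the hypothesis would add that lean to the estimate, and it could not be separated from a real effect afterwards.

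Two routes are easy to picture. A microphone in a room with broadband sound might show a change at lights off, and because each subject has one night of each kind, recognising one night identifies the other. An operator's note that the sound was turned down would also reveal the condition. The plan mentions no coded files, hidden channels, screened notes or locking of scores before the key is opened. The only access rule, in section IX, keeps out people from outside the research team.

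**Working it through.** The plan gives no figure on this point, so there is none to reproduce. The first four steps set the text side by side; the fifth checks the size a bias could have.

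**1. What the masking covers.** Each subject contributes one sound night and one quiet night. Order and condition then carry the same information for anyone who knows which night came first. Masking to order is therefore masking to condition in practice, and rewording the statement would change nothing a scorer does.

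**2. Whether the operator could be the scorer.** The operator is a co-investigator or trained student; the scorer is an expert technologist. The plan does not say in so many words that these must be different people. But whoever switches the sound on knows the condition that night, and so cannot meet the masking statement. That statement already excludes the operator.

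**3. Whether the recording reveals the condition.** Three things must all be true for the microphone route:

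- the sensor on the neck visibly or audibly registers 40 dB sound (350 to 4000 Hz) from wall-mounted speakers;
- that channel is shown to the scorer;
- the scorer acts on it despite standard rules.

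The documents establish none of these. They give no sensitivity, bandwidth or sampling rate for the sensor, and the signals named for staging and arousals do not include it. For the notes route, the plan does not say that such notes are written into the file or passed to the scorer.

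**4. Which outcomes are exposed.** Only the scored ones. The subjective sleep quality score and the Stanford Sleepiness Scale do not pass through the technologist.

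**5. What a bias would do if it existed.** Inputs from the documents: n = 20 (section III) and a 0.05 threshold with a Student t-test (section VI). Assumptions: a paired, two-sided test, and a systematic scoring shift of 0.1, 0.2 or 0.3 SD of the paired differences.

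With no true effect, the rejection probability comes from the noncentral t with df = 20 − 1 = 19, critical value 2.093 and noncentrality shift × √20:

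| Assumed shift (SD) | Noncentrality | False-positive rate |
|---|---|---|
| 0 | 0 | 5.0% |
| 0.1 | 0.447 | 7.1% |
| 0.2 | 0.894 | 13.6% |
| 0.3 | 1.342 | 24.7% |

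Now suppose a true effect of 0.3 SD (also assumed) and a later paired study sized for 80% power on the inflated estimate. Unbiased planning would need 90 subjects.

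| Expected estimate (SD) | Planned n | Actual power at 0.3 SD |
|---|---|---|
| 0.3 + 0.1 = 0.4 | 52 | 56.5% |
| 0.3 + 0.2 = 0.5 | 34 | 39.7% |
| 0.3 + 0.3 = 0.6 | 24 | 29.1% |

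For scale, the approximate 95% half-width of a standardized paired effect at n = 20 is 2.093 / √20 = 0.47 SD, which exceeds every shift in the table. A later study sized on this pilot would be poorly determined even with perfect masking.

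These tables show what any systematic error of that size would do, whatever its source. They give no evidence that such an error is present here.

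**The case for a change.** The best argument for a change is that a promise without a method cannot be checked by a reader, while the remedy is cheap: about 20 × 2 = 40 files, coded, with the microphone channel and any sound-related notes hidden, and scores locked before the key is opened. Hiding the microphone would remove no signal named for staging or arousals, and snoring is not a listed outcome. Scoring rules narrow discretion without abolishing it. Pilot status is no excuse either, since the estimate is what the study is meant to deliver.

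Much of this stands. No procedure is written down, the suggested steps are good practice, and a sentence describing them would help a reader. It does not follow that the plan is defective. The commitment is made twice, and keeping revealing material from the scorer is part of honouring it. File coding and channel display are ordinarily settled in laboratory procedures, and their absence from a short protocol does not show that they are absent in practice. Some of the proposed steps add little: a study date reveals nothing about condition without the allocation list, and a bar on the operator scoring is already implied.

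**Conclusion.** The concern does not call for a change. The plan commits to masked scoring under a recognised standard, and a team that carries out that commitment obtains masked scores. What is missing is detail that analysts and laboratory staff fill sensibly. A line on how the masking is maintained would be an optional clarification.

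No size can be attached to the risk from the documents. The illustrative range, false positives of 7.1% to 24.7% instead of 5%, depends wholly on assumed shifts of 0.1 to 0.3 SD and on a paired two-sided test that section VI does not specify.

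The conclusion rests on two readings: that masking to order means masking to condition in this two-night design, and that the masking statement is to be followed as written. It would change if there were evidence that the scorer sees a channel or note that reveals the sound, and the documents contain none.

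### Does the undefined rule for repeating nights with insufficient data leave the analysed data open to choice?

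*Combined protocol and SAP*

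**What the plan says.** Repeats are mentioned in two places, both in Section V. Under Data Analysis: "If the data collected will be considered insufficient, the subject will be asked to repeat the whole study or a part of it". Under Reimbursement, payment for extra nights applies thus: "If the subjects will repeat a part or the entire protocol because of insufficient data collection". Neither place gives a threshold, a decision-maker, a limit on repeats or a rule for which recording enters the comparison, and no other section supplies one.

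The related provisions are:

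- Scoring (Section V, Data Analysis): "Sleep will be scored by an expert sleep technologist blinded to the randomization order following American Academy of Sleep Medicine rules".
- Self-reported outcomes (Section V, Protocol): "Stanford Sleepiness Scale score and a subjective sleep quality score will be obtained from every subject after each study night".
- Overnight staff (Section V, Measurements and equipment): the co-investigator or student who switches the sound on also watches the recordings, and so knows the condition.
- Oversight (Section IX): "The PI will be responsible for monitoring safety and quality assurance"; in addition, "the ongoing results, problems, and limitations of the study will be presented on a regular basis to the investigators" of the sleep division.
- Purpose (Section VI): "In this protocol we want to collect pilot data to measure the possible size effect of this intervention", with a Student t-test at p<0.05.

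**The concern.** The repeat rule decides which nights count, and it has no stated criterion. Even if every repeat is for a technical reason, there are two ways to end with more than one usable value for a condition.

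1. If the whole study is repeated after one failed night, the other condition has two good recordings.
2. The sleepiness and subjective quality scores do not need the polysomnography signals. A night repeated because a recording failed can therefore leave two valid scores for one condition. This is not always so: if the sound system failed, or the questionnaire itself was missing, there is only one.

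The aim in Section II lists "subjective sleep quality scores, sleep onset latency, sleep architecture" in that order, so the self-reported outcome comes first. The stated blinding covers the scorer, who is not given the repeat decision, while the person watching the recordings knows the condition. A choice between values could therefore be made by someone who knows the condition and perhaps the results. The study exists to estimate an effect size, and each subject is 1/20 = 5% of the sample, so even a few such choices might matter.

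**Working it through.** The plan gives no power calculation, SD or repeat rate, so it has no figure of its own to reproduce. The question is how much the open choice could move the result.

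**Inputs.** From the documents: 20 subjects, two nights each in random order, t-test at 0.05. Assumed: the test is paired and two-sided; the between-night correlation ρ is 0.5 (range 0.3 to 0.7); k = 1, 2 or 3 subjects repeat (5%, 10% or 15% of 20). The unit is the between-subject SD of one night's value.

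**Standard error of the effect.** √(2(1−ρ))/√20 = 1/4.472 = 0.22 at ρ = 0.5.

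**First value against repeat value, duplicates in one condition.** Each such subject changes the mean difference by (repeat − first)/20, and repeat − first has SD √(2(1−ρ)). For k subjects the two estimates differ by an SD of √k × √(2(1−ρ))/20.

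**Duplicates in both conditions.** This applies to self-reported scores after a whole-study repeat. The variance per subject doubles, giving √(2k) × √(2(1−ρ))/20.

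| SD of the difference between estimates | k=1 | k=2 | k=3 |
|---|---|---|---|
| One condition, ρ=0.3 | 0.059 | 0.084 | 0.102 |
| One condition, ρ=0.5 | 0.050 | 0.071 | 0.087 |
| One condition, ρ=0.7 | 0.039 | 0.055 | 0.067 |
| Both conditions, ρ=0.5 | 0.07 | 0.10 | 0.12 |

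Relative to the standard error, the one-condition figure is √(k/20) whatever ρ is: 0.22, 0.32 and 0.39.

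**Simulated error rates at ρ = 0.5 (k = 1/2/3).**

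- *Technical repeats, any one rule applied throughout (first, repeat or mean):* bias 0.00, type I error 4.9–5.1%.
- *Technical repeats, first against repeat, duplicates in one condition:* the p<0.05 verdict differs in 2.0/2.9/3.6% of trials with no effect, and in 4.7/7.0/8.7% at the effect with 80% power (0.66 SD).
- *Any of first, repeat or mean may be reported if significant:* type I error 6.0/6.5/6.8% with duplicates in one condition, 6.3/7.2/7.6% with duplicates in both.
- *The worst 1/2/3 sound nights replaced because the subject slept badly:* false benefit 0.05/0.08/0.11 SD, type I error 5.8/7.0/8.2%. Over ρ from 0.3 to 0.7 the ranges are 0.03–0.15 SD and 5.4–9.8%.

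Only the last two cases raise the error rate. One needs a value chosen for its result; the other needs *insufficient* to mean poor sleep.

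**Which case does the text support?** The Reimbursement sentence ties repeats to the collection of data, which describes a recording that failed. Nothing in the protocol makes short or broken sleep a ground for a repeat, and nothing suggests picking between values by result.

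**The case for a change.** The best case for a change is that it would be almost free. A few sentences could limit repeats to technical failure, let the blinded scorer judge signal adequacy before sleep variables are computed, keep every usable night, and report repeats by condition. Pilot status is a weak defence where the effect estimate is the product. Repeats may also be common: if 2% or 5% of the 40 nights failed (assumed rates), the chance of at least one failure would be 1 − 0.98^40 = 55% or 1 − 0.95^40 = 87%. And the protocol does not say whether a night on which the sound was reduced or stopped for intolerance (Section VII) counts as insufficient; that can happen only in the sound condition.

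The omissions are real, and the repeat decision is not stated to be blind. Three things limit what follows.

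- The harm comes from misuse that no text suggests, not from the missing detail itself.
- The Section IX passages on quality assurance and on presenting results are general and are not linked to repeats. The better evidence on blinding is the role of the overnight staff, and it shows knowledge of the condition, not selection.
- Added wording would still need a numerical threshold for an unscorable recording, and the documents give no basis for one. Once usable nights are kept, a sensitivity analysis on first nights would only repeat the main analysis for the polysomnography outcomes.

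**Conclusion.** No change to the plan follows. The protocol omits a detail that analysts fill in the ordinary way: replace the night that failed, keep the nights that worked, and say so in the report. Any such rule, applied without regard to results, gives no bias and a type I error of about 5%. What remains open moves the estimate by an SD of 0.05 to 0.12 against a standard error of 0.22, in a study whose declared purpose is a pilot estimate.

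These sizes assume 1 to 3 repeats, ρ = 0.5 and a paired two-sided test. Absence of bias also assumes that repeat nights are exchangeable with first nights, so that an extra laboratory night has no order effect of its own. That assumption deserves notice if repeats fall mainly in one condition, as sound-system failures would. The conclusion would differ if there were evidence that nights were repeated for how the subject slept; the documents contain none. A count of repeats by condition, with reasons, would let a reader of the results check this.

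### Does Section VI need to say that the t-test is paired and define the effect size the pilot is meant to measure?

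*Combined protocol and SAP*

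**What the plan says.** Section VI (Biostatistical Analysis) has two sentences. The first gives the purpose: "In this protocol we want to collect pilot data to measure the possible size effect of this intervention". The second gives the method: "Variables of interest will be compared using a Student T-test with" p<0.05 as the significance level.

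The variables are found in Section II (Specific Aims): "subjective sleep quality scores, sleep onset latency, sleep architecture (time spent in rapid eye movement (REM) and non-REM (NREM) sleep stage 1, 2, 3"), together with "number of arousals from sleep and time of wakefulness after sleep onset in a group of healthy subjects". The same section states a directional hypothesis, "We hypothesize that the exposure to sound during sleep will improve sleep quality and will reduce sleep onset latency", and introduces the list of variables with "Specifically, we will test this hypothesis by assessing". A test therefore fits the aims.

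The design is in Section V (Study Procedures): "The protocol will be composed by 2 overnight sleep studies (a night with no noise and a night with background noise"), about a week apart and in random order. The sample size is in Section III: "We will recruit a group of 20 healthy controls aged 21 to 65 years old". No SD, correlation, expected effect, power or precision target is given anywhere.

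**The concern.** A plan whose declared product is an effect size would be expected to say what that effect size is. Section VI leaves three things open:

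- **Pairing.** The name Student t-test covers both the paired and the two-sample test, and the two give different intervals and p-values on the same data.
- **The effect size.** It could be a raw difference, a difference divided by the SD of the within-subject differences, or a difference divided by the single-night SD. The last two can differ noticeably.
- **Sidedness.** The hypothesis is directional, and the 0.05 level is not said to be one- or two-sided.

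If these were truly undecided, the significance label and any standardised effect could depend on a choice made after the data were seen. A later team might also size a trial on a number whose denominator it did not know.

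**Working it through.** **Inputs from the documents:** 20 subjects (Section III); both nights in each subject (Section V); Student t-test, 0.05 level (Section VI). The 20 comes with no derivation, so there is no figure of the plan's own to reproduce.

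**Assumptions, not in the documents:** two-sided 95% intervals, equal SD on both nights (set to 1), night-to-night correlation ρ from 0.3 to 0.7, roughly normal differences, complete pairs unless stated.

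**1. Paired half-width in SD of the differences,** t(0.975, n−1)/√n. This needs no ρ.
- 20 pairs: 2.093/√20 = 0.468
- 18 pairs: 2.110/√18 = 0.497
- 16 pairs: 2.131/√16 = 0.533

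**2. Half-widths in single-night SD.** Paired: 2.093 × √(2(1−ρ)/20). Unpaired, 20 against 20 nights: t(0.975, 38) × √(2/20) = 2.024 × 0.316 = 0.640.

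| ρ | Paired | Unpaired | Unpaired ÷ paired |
|---|---|---|---|
| 0 | 0.662 | 0.640 | 0.97 |
| 0.3 | 0.554 | 0.640 | 1.16 |
| 0.5 | 0.468 | 0.640 | 1.37 |
| 0.7 | 0.363 | 0.640 | 1.77 |

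**3. When the significance label would differ.** Unpaired: t = d/√(2/20) on 38 df. Paired: t = d/√(2(1−ρ)/20) on 19 df. Here d is the observed difference in single-night SD, and p is two-sided.

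| d | Unpaired p | Paired p, ρ 0.3 | ρ 0.5 | ρ 0.7 |
|---|---|---|---|---|
| 0.3 | 0.35 | 0.27 | 0.20 | 0.10 |
| 0.5 | 0.12 | 0.074 | 0.038 | 0.009 |
| 0.7 | 0.033 | 0.016 | 0.006 | 0.001 |

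The label changes only when d lies between the paired and unpaired half-widths: 0.55 to 0.64 at ρ 0.3, 0.47 to 0.64 at ρ 0.5, and 0.36 to 0.64 at ρ 0.7. Outside that band both tests agree.

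**4. Standardised effect for d = 0.5.** Over the single-night SD it is 0.50. Over the SD of the differences it is 0.5/√(2(1−ρ)) = 0.42, 0.50 and 0.65 at ρ 0.3, 0.5 and 0.7.

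**5. Sidedness.** At d = 0.5 and ρ 0.3, the paired p of 0.074 two-sided becomes 0.074/2 = 0.037 one-sided.

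**6. Setting the sections side by side.** Section V produces two measurements per subject under two conditions. Section VI compares those conditions. The only t-test that respects this structure is the paired one, and nothing in the protocol points to treating the 40 nights as independent. The raw difference, the SD of the differences and the SD on each night all come from the same 20 pairs of values, so every version of the effect size can be computed and labelled when results are written up.

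**The case for a change.** The strongest case for a change is that even a reader who takes pairing for granted still does not know which effect size will be reported, and Section VI commits only to a p-value. Pilot effects are often used to plan a later study. For a two-sided 5% paired t-test with 80% power, standardised effects of 0.423, 0.50 and 0.645 over the SD of the differences need 46, 34 and 21 pairs. Someone who took a 0.50 based on the single-night SD for the paired effect would plan 34 pairs when 46 or 21 were needed. A few words would remove the doubt at almost no cost.

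The arithmetic stands, and so does the point that any standardised effect should name its denominator. But the protocol promises no standardised effect, so the misled reader is hypothetical, and the remedy lies in how results are reported. Adding the word paired and a general promise to name the SD would still leave the denominator and the sidedness to be chosen at analysis, so light clarifying text gains little.

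One complication also remains. Paired and unpaired tests share the same mean difference only if every subject completes both nights. Withdrawal is allowed, and an unpaired test could use single nights that a paired test drops. Section V's provision for repeating nights with insufficient data helps with failed recordings, though not with withdrawals.

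**Conclusion.** No change is needed. Section VI is terse: it does not say paired or two-sided and does not define the effect size. The two-night within-subject design supplies the first, two-sided testing is the usual default for an unqualified 0.05 level, and the mean within-subject difference with its SD and interval is what an analyst would report from a pilot of this kind. No stated rule or number is shown to be wrong.

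The firm figure is a half-width of 0.468 SD of the differences with 20 complete pairs (0.497 with 18, 0.533 with 16), which needs no correlation but is simply t/√n. The contrast with 0.64 single-night SD, and the 1.16 to 1.77 ratio, rest on an assumed correlation of 0.3 to 0.7, equal SDs, complete pairs and an unpaired analysis that no section proposes. At zero correlation the contrast disappears. Approximate normality is also assumed; the documents do not show it for sleep latency, wake after sleep onset or arousal counts.
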